5. Willingness to utilize two reliable forms of contraception (for both males and females of childbearing potential) from Screening to one month after the last dose of study drug

Key Exclusion Criteria:

1. Known active infection with hepatitis B virus (HBV) and/or human immunodeficiency virus (HIV)
2. History of renal transplant and/or severe renal impairment defined as eGFR (estimated glomerular filtration rate) of less than 30 mL/min/1.73 m²
3. Evidence of tumor burden >Milan criteria, or evidence of micro- or macrovascular invasion in explanted liver
4. Hepatocellular carcinoma (HCC) at entry into the study
5. Concurrent sirolimus (rapamycin) use

Title: A Multicenter, Double-Blind, Randomized Trial of IDN-6556 in Subjects Who had Hepatitis C Virus (HCV) Reinfection and Liver Fibrosis or Cirrhosis following Orthotopic Liver Transplantation for Chronic HCV Infection and Who Subsequently Achieved a Sustained Virologic Response Following anti-HCV Therapy

6. History or presence of clinically concerning cardiac arrhythmias, or prolongation of Screening (pre-treatment) QTcF interval of > 480 milliseconds (msec)
7. Subjects with diagnosed or suspected systemic lupus erythematosus (SLE) and/or rheumatoid arthritis (RA)
8. If female: known pregnancy, positive urine or serum pregnancy test, or lactating/breastfeeding.

Criteria for Evaluation:**Safety Variables:**

Safety evaluations will be based on adverse event (AE) reports. These will be coded using MedDRA to preferred terms, sorted by body system, and compared between the two treatment groups.

1. Serious adverse events will be analyzed separately
2. Clinical laboratory variables will be evaluated in the context of coinciding clinical adverse events when necessary

Efficacy Variables:Efficacy Endpoints:

- Ishak Fibrosis Score
- Necro-inflammatory sub-score of the modified Histological Activity Index
- Biomarkers of apoptosis
- Liver function (e.g., ALT, AST, bilirubin)
- Transient elastography (to be performed at select centers only)

Exploratory Endpoint:

- Morphometric image analysis to quantify collagen deposition

Statistical Methods:

All endpoints will be tested at a two-sided statistical significance level of 0.05.

For the comparison of Ishak Fibrosis Scores at 24 months, subjects will be classified into one of the following three categories:

- Category 1. Regression at 24 months defined as a greater than or equal to a one point improvement in Ishak Fibrosis Score from Baseline.

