4.2 Study Rationale

The Investigator's Brochure (IB) contains a summary of the data and information collected about IDN-6556 (including principal data and findings from preclinical, toxicological, and clinical studies conducted to date).

IDN-6556 is a novel small molecule irreversible caspase inhibitor. Caspases are enzymes responsible for executing apoptotic pathways, or programmed cell death, and activating cytokines such as IL-1 β and IL-18. The apoptotic pathway has been previously shown to play an important role in the formation and progression of hepatic fibrosis, leading to the hypothesis that inhibition of caspases may have significant therapeutic benefit for the treatment of liver fibrosis, independent of the underlying disease state (e.g., viral infection, fatty liver, etc.). Activation of pro-inflammatory cytokines such as IL-1 β has also been shown to play a role in hepatic injury. IDN-6556 has shown specificity in assays measuring caspase inhibition, and prevented apoptosis in a variety of cellular assays. IDN-6556 demonstrated efficacy in a number of animal models of liver disease, as well as in models of damage to other organ systems. Human studies have demonstrated that IDN-6556 can lower serum transaminases after intravenous or oral administration. Treatment with IDN-6556 was also associated with statistically significant reductions in elevated activated serum caspases and cCK18, a caspase cleaved substrate, indicating that IDN-6556 works by the presumed mechanism of action of inhibiting caspases.

In subjects who received a liver transplant and were successfully treated and achieved an SVR, fibrosis and inflammation were still present up to 5 years after treatment^{9,10,11}. In general, fibrosis stabilized or regressed in most subjects with increases in fibrosis in only a small subset of subjects. In general, inflammation/necro-inflammation was still present, but reduced as compared to pre-treatment. A caspase inhibitor, such as IDN-6556, could have clinical utility by reducing apoptosis rates and inflammation, which would also reduce the stimulus for fibrogenesis. Given this rationale, this study will evaluate the efficacy and safety of IDN-6556 in subjects with chronic hepatitis C virus (HCV) infection who have undergone

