12.5 Sample Size

The sample size determination for this study is based on the Phase 2b screening methodology presented in Fleming and Richardson¹².

A total of 60 subjects will be treated in a 2:1 ratio to IDN-6556 or placebo. Treatment duration for all subjects will be two years. The primary outcome variable is change in Ishak Fibrosis Score at 24 months.

The primary analysis of this Phase 2 “screening” study is formally based on a three-category decision guideline. To be specific, the decision guideline for this study is based on whether the proportion of subjects who show a regression (i.e., improvement) of Ishak Fibrosis Score at 24 months for the IDN-6556 arm compared to the placebo arm is less than 5%, is from 5% up to 15%, or is at least 15%.

Note that these categories should not be interpreted as providing strict decision rules but rather as guidelines that will be factored into a broader scientific assessment of the benefit to risk profile of the IDN-6556 regimen. This broader assessment will include consideration of safety, of secondary efficacy endpoints, and of relevant information external to this study. Specifically, the decision guidelines for this study are:

1. If the estimated absolute increase in the proportion of subjects who show regression in Ishak Fibrosis Score is less than 5%, (e.g., less than an estimated increase from 30% to 35%), then the IDN-6556 regimen is not plausibly more efficacious than placebo; the formulation of this IDN-6556 regimen or its utility in this indication will be reconsidered.
2. If the estimated absolute increase in the proportion of subjects who show regression in Ishak Fibrosis Score is from 5% up to 15%, (e.g., an estimated increase from 30% to between 35% and 45%), then the IDN-6556 regimen is

Title: A Multicenter, Double-Blind, Randomized Trial of IDN-6556 in Subjects Who had Hepatitis C Virus (HCV) Reinfection and Liver Fibrosis or Cirrhosis following Orthotopic Liver Transplantation for Chronic HCV Infection and Who Subsequently Achieved a Sustained Virologic Response Following anti-HCV Therapy

plausibly more efficacious than placebo and if analyses of biomarkers suggest utility of the IDN-6556 regimen, should be evaluated definitively in a subsequent Phase 3 clinical study.

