3. If the estimated absolute increase in the proportion of subjects who show regression in Ishak Fibrosis Score is at least 15%, (e.g., an estimated increase from 30% to greater than 45%), then the IDN-6556 regimen will be evaluated definitively in a subsequent Phase 3 study.

The operating characteristics for this three-category decision guideline (based on 100,000 simulated trials) are shown in the table below.

Table 12.1 Probabilities of Study Outcomes According to Various Levels of True Treatment Effect (TE)

| TE | Probability of obtaining an estimated TE (active – placebo) | | |
|----|---|-----------------|------|
| | <5% | Of >5% but ≤15% | >15% |
| 0 | 67% | 22% | 11% |
| 5 | 52% | 26% | 22% |
| 10 | 36% | 27% | 37% |
| 15 | 23% | 24% | 53% |
| 20 | 13% | 19% | 68% |
| 25 | 7% | 13% | 80% |
| 30 | 3% | 8% | 89% |

Of note:

1. The false-positive error rate of the screening procedure is low. In particular, if the IDN-6556 regimen truly provides no improvement in the 2-year Ishak Fibrosis Score, then there is only an 11% chance of going forward to a Phase 3 study and only a 2.5% chance of false positive conclusion that the IDN-6556 regimen has statistically significant improvement in efficacy relative to placebo.
2. The false-negative error rate is acceptable. If the IDN-6556 regimen truly provides an absolute increase of 15%, (e.g., an increase from 30% to 45%), then there is only a 23% chance that the combination intervention would be discarded, and thus a 77% chance that it would be evaluated in a subsequent Phase 3 study. If the true absolute increase is 15%, there is a 20% chance that the IDN-6556 regimen will have a statistically significant improvement in efficacy relative to placebo and a 80% chance of a statistically significant difference if the true absolute increase is 37% (at the 2-sided 0.05 level).

Title: A Multicenter, Double-Blind, Randomized Trial of IDN-6556 in Subjects Who had Hepatitis C Virus (HCV) Reinfection and Liver Fibrosis or Cirrhosis following Orthotopic Liver Transplantation for Chronic HCV Infection and Who Subsequently Achieved a Sustained Virologic Response Following anti-HCV Therapy

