12.6.3 Efficacy Analysis

Primary Endpoint: Change from Baseline in Ishak Fibrosis Score at 2-years

The primary analysis of the primary endpoint will test the change in Ishak Fibrosis Scores at 24 months between the treatment groups in the FAS Population using ITT principles.

Subjects will be classified into one of the following 3 categories:

- Category 1. Regression at 24 months defined as a greater than or equal to a one point improvement in Ishak Fibrosis Score from Baseline.

Title: A Multicenter, Double-Blind, Randomized Trial of IDN-6556 in Subjects Who had Hepatitis C Virus (HCV) Reinfection and Liver Fibrosis or Cirrhosis following Orthotopic Liver Transplantation for Chronic HCV Infection and Who Subsequently Achieved a Sustained Virologic Response Following anti-HCV Therapy

- Category 2. Stable disease at 24 months defined as no change from Baseline in the Ishak Fibrosis Score from Baseline.
- Category 3. Progression at 24 months defined as a greater than or equal to a one point worsening from Baseline in the Ishak Fibrosis Score from Baseline or death/re-transplantation.

Changes in the Ishak Fibrosis Score at 24 months will be analyzed by a logistic regression model, appropriate for the analysis of ordinal categorical data, to derive the odds ratio and associated 95% confidence interval for IDN-6556 against placebo. The model will allow adjustment for the following variables:

- Baseline Ishak Fibrosis Score
- Immunosuppression regimen (classified into one of five groups: tacrolimus with/without steroids; cyclosporine with/without steroids; other)
- Age of the transplant donor
- Age of the recipient

Subgroup analyses of the model covariates, stated above, will also be conducted.

Shift tables of changes in Ishak Fibrosis Score over time will also be presented.

Secondary Endpoint

Estimates of the treatment effect of IDN-6556 versus placebo, and corresponding 95% confidence intervals of the modified Histological Activity Score will be conducted applying the suitable model for ordinal categorical data and detailed in the Statistical Analysis Plan. Shift tables showing changes over time will also be presented.

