5 STUDY ENDPOINTS

5.1 PRIMARY EFFICACY ENDPOINT

The Ishak Fibrosis Score will be determined by liver biopsy as scored by the central histopathologist. The Ishak Fibrosis Score classification is defined as:

- 0 = No fibrosis (F0);
- 1 = Fibrous expansion of some portal areas, with or without short fibrous septa (F1);
- 2 = Fibrous expansion of most portal areas, with or without short fibrous septa (F2);
- 3 = Fibrous expansion of most portal areas, with occasional portal to portal bridging (F3);
- 4 = Fibrous expansion of portal areas, with marked bridging (F4);
- 5 = Marked bridging with occasional nodules (F5);
- 6 = cirrhosis probable or definite (F6).

Fibrosis scores of F0 and F1 will be excluded from enrollment. The change from baseline in the Ishak Fibrosis Score will be derived for each subject and will be used to classify subjects into one of the three following groups:

- Improvement, defined as having a reduction from baseline of at least 1-point in the Ishak Fibrosis Score
- Stable, defined as having no change from baseline in the Ishak Fibrosis Score
- Worsening, defined as having an increase from baseline in the Ishak Fibrosis Score

Subjects will be classified as a responder or non-responder based on the above three groups and their baseline Ishak Fibrosis score. The definition of response is based on the following:

- For subjects with baseline Ishak Fibrosis Score of F2-F5, achieving either improvement or remaining stable
- For subjects with baseline Ishak Fibrosis Score of F6, achieving improvement

The response at Month 24 will be used as the primary endpoint in this study. Response rates at Month 12 using the same definitions as above will also be summarized.

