9.2.2 Secondary Efficacy Analysis: Change from Baseline in Ishak Fibrosis Score

Changes from baseline for the Ishak fibrosis score will also be summarized descriptively by treatment group using a shift table.

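### The SAP drops the protocol's ordered regression/stable/progression comparison, so Ishak-scale improvement in F2-F5 subjects has no planned between-arm difference, confidence interval or test

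*SAP*

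**What the plan says.** **Protocol.** Section 12.6.3 places each subject at Month 24 in one of three ordered categories: regression, stable, or progression. Progression includes death and re-transplantation. The change is then "analyzed by a logistic regression model, appropriate for the analysis of ordinal categorical data, to derive the odds ratio and associated 95% confidence interval", active against placebo. Section 12.5 sizes the trial on one of those categories: "the decision guideline for this study is based on whether the proportion of subjects who show a regression (i.e., improvement) of Ishak Fibrosis Score" differs between arms by less than 5, 5 to 15, or at least 15 points. Its power statements concern the same quantity. They give 20% power at a 15-point gain and "a 80% chance of a statistically significant difference if the true absolute increase is 37" points.

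**SAP.** Section 5.1 makes the primary endpoint a binary response. One limb reads "For subjects with baseline Ishak Fibrosis Score of F2-F5, achieving either improvement or remaining stable"; for F6 subjects only improvement counts. Section 9.1 gives a risk difference with 95% CI for this response, and 9.2.1 adds stratified Cochran-Mantel-Haenszel (CMH) tests. For change in Ishak score, 9.2.2 says: "Changes from baseline for the Ishak fibrosis score will also be summarized descriptively by treatment group using a shift table". Section 9 also describes the components of the primary endpoint by arm, without comparison. Section 9.2.6 repeats the primary analysis for at least one stage of improvement after mapping Ishak to NASH CRN stages (Table 2 in 5.2.2). No ordinal model appears anywhere. Section 14.1 records the new primary endpoint and says the analysis was updated to match, but does not say that the ordinal model was removed.

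**The concern.** In F2-F5 the SAP response cannot tell a subject whose fibrosis regressed from one whose fibrosis did not change. The protocol's own rationale (4.2) makes that distinction important: "In general, fibrosis stabilized or regressed in most subjects with increases in fibrosis in only a small subset of subjects". If few untreated subjects worsen, extra regression on active drug must come largely from subjects who would otherwise have been stable. Such a move changes SAP response only in F6, and at most 15 of 60 subjects can be F6.

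At stake is whether the planned analysis can show the effect that the trial was sized on. A drug that turns stable fibrosis into regression could land in the lowest guideline band on SAP response, although the three-category data that show the effect are already collected. A regression comparison added after unblinding would be post hoc.

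**Working it through.** **Inputs from the documents.** Allocation: "A total of 60 subjects will be treated in a 2:1 ratio to IDN-6556 or placebo", so 40 and 20. Level: "All endpoints will be tested at a two-sided statistical significance level of 0.05". Placebo rate 30% (Protocol 12.5 examples; SAP 4). F6 cap 15 of 60, so F2-F5 is at least 60 − 15 = 45.

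**Assumptions.** Placebo worsening *w* in F2-F5 has no figure in the documents, so it is varied from 5% to 30%. Subjects are 30/15 in F2-F5 and 10/5 in F6 (active/placebo), with complete data. Placebo improvement is 30% in both groups.

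**Step 1: reproduce the protocol's power for regression.** Power = Φ[(Δ − 1.96·SE₀)/SE₁], with SE₀ = √{p̄(1−p̄)(1/20+1/40)} and SE₁ = √{p₁(1−p₁)/20 + p₂(1−p₂)/40}.

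- 30% to 67%: p̄ = (6 + 26.8)/60 = 0.547, SE₀ = 0.1363, SE₁ = 0.1266. Power = Φ[(0.37 − 0.2672)/0.1266] = Φ(0.81) = 79.2%.
- 30% to 45%: p̄ = 0.40, SE₀ = 0.1342, SE₁ = 0.1292. Power = Φ[(0.15 − 0.2630)/0.1292] = Φ(−0.87) = 19.1%.

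Exact enumeration of the uncorrected chi-square test gives 80.3% and 20.3%. The stated 80% and 20% are therefore powers for a difference in regression.

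**Step 2: translate the effect to SAP response.** The odds ratio for 30% to 67% is (0.67/0.33)/(0.30/0.70) = 4.74. Take *w* = 15%. Under proportional odds, the odds of not worsening rise from 0.85/0.15 = 5.67 to 26.8, so response in F2-F5 goes from 85% to 96.4%, a gain of 11.4 points. F6 gains 37. The pooled response difference is 0.75 × 11.4 + 0.25 × 37 = 17.8 points, less than half of the 37-point gain in regression.

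**Step 3: power** (100,000 simulated trials per scenario, significant in the improving direction at two-sided 0.05, stratified F2-F5 against F6). The response test is CMH; the ordinal test is van Elteren.

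| Scenario, regression 30% to 67% | SAP response | Ordinal |
|---|---|---|
| Proportional odds, *w* = 5% | 36% | 80% |
| Proportional odds, *w* = 10% | 43% | 81% |
| Proportional odds, *w* = 15% | 49% | 82% |
| Proportional odds, *w* = 20% | 55% | 82% |
| Proportional odds, *w* = 30% | 65% | 83% |
| Proportional odds, *w* = 15%, only 6 F6 subjects | 39% | 82% |
| Gain only from stable, *w* = 15% | 13% | 65% |

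A CMH test of improvement alone has about 80% power throughout, because it depends only on the improvement rates. With no effect, rejection is 2.7% (response), 2.2% (improvement) and 2.5% (ordinal).

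**Step 4: the guideline bands.** For a true 15-point gain taken only from stable subjects, the mean response difference is 0.25 × 15 = 3.75 points. About 50% of trials then fall below 5 points, against 19% when regression itself is measured. (Protocol Table 12.1 shows 23% for this cell. Exact counting gives 19.1%; 22.8% arises when some differences of exactly 5 points fall below the cut-off through floating-point rounding.)

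**Step 5: what the mapped analysis recovers.** In SAP Table 2, Ishak F3 and F4 share a stage, and so do F5 and F6. Falls from F4 to F3 and from F6 to F5 are therefore not counted; F2 to F1, F3 to F2 and F5 to F4 are. If 50-85% of Ishak regressions survive the mapping (assumed), power at 30% to 67% is 33-67%. If all survive, it is 80%.

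**The case against.** A reader might infer that regression has no between-arm estimate at all, or that response is the only endpoint compared. SAP 9.2.6 rules that out. It repeats the primary analysis, which includes a risk difference with 95% CI, for improvement alone at Months 12 and 24, and most one-point Ishak falls in F2-F5 still count. The fall from F6 to F5, which the mapping misses, counts as response in the primary endpoint. This stands, and it narrows the gap to the unmapped Ishak scale in F2-F5. It does not close the gap. The mapped scale is coarser, its stated purpose is comparison with NASH trials, and the SAP leaves unclear whether it uses multiple imputation (the repeated primary analysis) or observed cases (9.2 and 12).

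A reader might also infer that most of the power is lost. That holds if the gain comes only from stable subjects, or just about with six F6 subjects. It fails in the 15% base case (82% to 49%, a relative loss of 40%) and at 30% worsening (83% to 65%).

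Two further points stand in part. First, this is a screening trial read on point-estimate bands that are guidelines only, and even regression had just 20% power at 15 points. But Step 4 shows that the bands are affected too. Second, Protocol 12.1 lets the SAP modify the plan, and 14.1 discloses the new endpoint. The change is therefore permitted; what is missing is an explicit statement that the ordinal comparison was dropped, and a reason.

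**Conclusion.** The point holds in this form. The protocol's ordinal odds ratio is absent from the SAP. In F2-F5, at least 45 of 60 subjects if 60 enrol, Ishak improvement of at least 1 point has only descriptive tables. The mapped NASH CRN analysis is the one remaining comparison of improvement alone across all stages.

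For the protocol's 30% to 67% effect, power on SAP response is substantially reduced: about 36-65% against 80-83% under proportional odds with 25% F6, and about 13% against 65% if only stable subjects move. These figures rest on assumed worsening rates, complete data and a two-level stratification. The documents say only that increases are uncommon, so the size of the loss cannot be fixed more closely. This should be corrected before unblinding, but as a supportive addition; it does not invalidate the primary analysis.

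**What to change.** In SAP 9.2.2, prespecify two supportive Month 24 analyses beside 9.2.6:

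- **(a)** the risk difference with 95% CI for unmapped Ishak improvement of at least 1 point;
- **(b)** the protocol's ordinal odds ratio with 95% CI (or a van Elteren test) on improved/stable/worsened, stratified by F2, F3-F5 and F6.

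Use the primary analysis's multiple imputation for both, with observed cases as sensitivity. Classify death and re-transplantation as worsening, as Protocol 12.6.3 does; SAP 5.1 is silent on them. They then count as not improved in (a). F6 subjects cannot worsen on a scale that ends at 6, so either check proportional odds or use the van Elteren test and let (a) carry the estimate. Record in SAP 14 that the ordinal model was removed and is restored, and whether the protocol's other covariates are kept.

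The primary endpoint is unchanged and no new data are needed. The cost is SAP wording, two tables, and further supportive comparisons without multiplicity adjustment.

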9.2.3 Secondary Efficacy Analysis: Ishak Modification of Knodell Histological Activity Index

The four components of the Knodell Histological Activity Index (interface hepatitis, confluent necrosis, parenchymal injury, and portal inflammation) will each be summarized descriptively by treatment group in two formats. The first format is descriptively summarizing each category by treatment group and visit. The second format is descriptively summarizing the shift in categories between baseline and Months 12 and 24, separately, by treatment group.

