8.2.2 Secondary

The secondary efficacy endpoint will be the effects on liver inflammation measured by the difference in responder rates in the necro-inflammatory sub-score of the modified Histological Activity Index between the two treatment groups (change defined as a movement by at least 2 points at 24 months compared with Baseline).

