12.2.2 Efficacy Variables

The following parameters will be recorded for the efficacy evaluation:

- Histologic changes defined as ≥ 1 point change in the Ishak Fibrosis Score
- Effects on liver inflammation in the necro-inflammatory sub-score of the modified Histological Activity Index. A responder will be defined as a subject who has improved by at least 2 points at 24 months on the necro-inflammatory sub-score of the modified Histological Activity Index from Baseline.
- Clinical outcomes defined as time to clinical worsening. Time to decompensation, re-transplantation, and/or death will be captured as clinical outcomes. (Note: Decompensation is defined as presence of: bleeding varices, encephalopathy, ascites requiring treatment and jaundice.)
- Effects on biomarkers of apoptosis and mechanism of action
- Effects on liver function parameters such as ALT, AST, bilirubin
- Changes in transient elastography (at select centers)

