APPENDIX II: LIVER BIOPSY SCORING AND ASSESSMENT

Ishak Modified Histological Activity Index (Ishak Fibrosis Score)

Liver biopsy findings are assigned scores for fibrosis as follows:

Table II.1 Ishak Fibrosis Score: Architectural Changes, Fibrosis and Cirrhosis

| | Score |
|--|-------|
| No fibrosis | 0 |
| Fibrous expansion of some portal areas, with or without short fibrous septa | 1 |
| Fibrous expansion of most portal areas, with or without short fibrous septa | 2 |
| Fibrous expansion of most portal areas, with occasional portal to portal bridging | 3 |
| Fibrous expansion of portal areas, with marked bridging (portal to portal as well as portal to central) | 4 |
| Marked bridging (portal to portal and/or portal to central) with occasional nodules (incomplete cirrhosis) | 5 |
| Cirrhosis probable or definite | 6 |

Ishak Modification of Knodell Histological Activity Index

Liver biopsy findings will be assigned scores for necro-inflammation as follows:

Table II.2 Ishak Modification of Knodell Histological Activity Index: Necro-inflammatory Scores

| | Score |
|--|-------|
| A Periportal or periseptal interface hepatitis (piecemeal necrosis) | |
| Absent | 0 |
| Mild (focal, few areas) | 1 |
| Mild/moderate (focal, most portal areas) | 2 |
| Moderate (continuous around <50% of tracts or septa) | 3 |
| Severe (continuous around >50% of tracts or septa) | 4 |
| B Confluent necrosis | |
| Absent | 0 |
| Focal confluent necrosis | 1 |
| Zone 3 necrosis in some areas | 2 |
| Zone 3 necrosis in most areas | 3 |
| Zone 3 necrosis + occasional portal-central bridging | 4 |
| Zone 3 necrosis + multiple portal-central bridging | 5 |

Title: A Multicenter, Double-Blind, Randomized Trial of IDN-6556 in Subjects Who had Hepatitis C Virus (HCV) Reinfection and Liver Fibrosis or Cirrhosis following Orthotopic Liver Transplantation for Chronic HCV Infection and Who Subsequently Achieved a Sustained Virologic Response Following anti-HCV Therapy

| | |
|---|---|
| Pan acinar or multiacinar necrosis | 6 |
| C Focal (spotty) lytic necrosis, apoptosis and focal inflammation | |
| Absent | 0 |
| One focus or less per 10X objective | 1 |
| Two – Four foci per 10X objective | 2 |
| Five – Ten foci per 10X objective | 3 |
| More than ten foci per 10X objective | 4 |
| D Portal Inflammation | |
| None | 0 |
| Mild, some or all portal areas | 1 |
| Moderate, some or all portal areas | 2 |
| Moderate/marked, all portal areas | 3 |
| Marked, all portal areas | 4 |

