2.2 SECONDARY OBJECTIVES

The secondary objectives of this clinical trial are:

- To determine the effects of oral emricasan on necro-inflammatory sub-score of the modified Histological Activity Index
- To determine the effects of oral emricasan on markers of mechanism of action and inflammation
- To assess the safety and tolerability of oral emricasan in subject's status post orthotopic liver transplantation.

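### The SAP plans no sub-score, responder definition or between-arm estimate for the protocol's one named secondary efficacy endpoint, and its change log does not say so

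*SAP*

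**What the plan says.** **Protocol.** Section 8.2.2 names a single secondary efficacy endpoint: "the difference in responder rates in the necro-inflammatory sub-score of the modified Histological Activity Index between the two treatment groups", with a threshold of 2 points at 24 months. Section 12.2.2 fixes the direction: "A responder will be defined as a subject who has improved by at least 2 points at 24 months". Section 12.6.3, under its secondary endpoint heading, promises "Estimates of the treatment effect of IDN-6556 versus placebo, and corresponding 95% confidence intervals of the modified Histological Activity Score", to be obtained by "applying the suitable model for ordinal categorical data and detailed in the Statistical Analysis Plan". It adds: "Shift tables showing changes over time will also be presented". Appendix II lists the four scored items ("Liver biopsy findings will be assigned scores for necro-inflammation as follows") but states no total.

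**SAP.** Section 2.2 retains the objective: "To determine the effects of oral emricasan on necro-inflammatory sub-score of the modified Histological Activity Index". Section 5.2.1 lists the four items and their categories, to be assessed at Months 12 and 24, and stops there. Section 9.2.3 says the four components "will each be summarized descriptively by treatment group in two formats"; the formats are category counts by visit, and shifts from baseline to Month 12 and to Month 24. Section 9.2 sets observed cases as the rule for secondary endpoints.

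**Change log.** On secondary analyses, SAP 14.1 records only the use of observed cases in the FAS, and it describes everything not listed as added detail and clarity. SAP 14.2 does not mention the activity index.

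**The concern.** The protocol hands the SAP a specific task: an effect estimate with an interval for a defined endpoint, with the modelling details to follow. The SAP keeps the objective and the shift tables but drops the estimate, and a reader of Section 14 would not learn this.

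Three things are at stake.

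- Following the SAP exactly, the study reports no treatment comparison for its named secondary efficacy endpoint, although SAP Section 4 says secondary efficacy analyses will feed the broader benefit-risk assessment.
- If the endpoint is later derived from the subject listings, the way the sub-score is formed and the model would be chosen after unblinding. Threshold, time point and direction are already fixed by the protocol.
- The priorities look inverted. SAP 9.2.6 repeats the full primary analysis, including the risk difference with 95% interval of SAP 9.1, for a NASH CRN mapping that the protocol does not contain.

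**Working it through.** The claim is mainly textual, so the first step is to compare the two documents.

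| Element | Protocol | SAP |
|---|---|---|
| Objective on the necro-inflammatory sub-score | Yes (5.0) | Yes (2.2) |
| Sub-score as a single quantity | Used in 8.2.2 and 12.2.2; how it is formed is not stated | Not formed (5.2.1, 9.2.3) |
| Responder, at least 2 points better at Month 24 | Yes (8.2.2, 12.2.2) | Not defined |
| Between-arm difference in responder rates | Yes (8.2.2) | Not planned |
| Effect estimate with 95% interval, ordinal model | Yes (12.6.3) | Not planned |
| Shift tables | Yes (12.6.3) | Yes, by component only (9.2.3) |
| Record of the change | – | None (14.1, 14.2) |

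**Could another SAP section supply the comparison?** The Cochran-Mantel-Haenszel test in SAP 9.2.1 applies to the analyses of Section 9.1, which concern Ishak fibrosis response. SAP 12 says only that secondary endpoints are not imputed. SAP 9 promises listings by subject and visit, which hold the raw items but are not an analysis.

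**Could the component tables substitute?** If the sub-score is the sum of the four items, its range is 0 to 4 + 6 + 4 + 4 = 18. This is the natural reading of Appendix II, but an interpretation. Take 20 subjects and two components, with the other two unchanged:

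- Pattern A: 10 subjects change by (−1, 0) and 10 by (0, −1). Every total change is −1, so there are 0 responders.
- Pattern B: 10 subjects change by (−1, −1) and 10 by (0, 0). Ten totals change by −2, so there are 10 responders.

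In both patterns each component table shows 10 one-point improvements. The responder rate is 0% in A and 50% in B. Separate component tables therefore cannot recover it under the sum reading. On any reading, no between-arm estimate is planned.

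**How precise would the missing estimate be?** The documents give no responder rate, power or interval width for this endpoint, so there is no plan figure to reproduce. The inputs are 40 and 20 subjects (Protocol Table 7.1), the same assumed true rate *p* in both arms, and assumed missing biopsies of 0%, 10% or 20%.

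Half-width = 1.96 × √[*p*(1 − *p*)(1/*n*₁ + 1/*n*₀)]. For *p* = 0.3 with 40/20: 1.96 × √[0.21 × (0.025 + 0.05)] = 1.96 × 0.1255 = 24.6 points.

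| Assumed *p* | 40/20 | 36/18 (10% missing) | 32/16 (20% missing) |
|---|---|---|---|
| 0.1 | 16.1 | 17.0 | 18.0 |
| 0.2 | 21.5 | 22.6 | 24.0 |
| 0.3 | 24.6 | 25.9 | 27.5 |
| 0.4 | 26.3 | 27.7 | 29.4 |
| 0.5 | 26.8 | 28.3 | 30.0 |

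At *p* = 0.1 only about 20 × 0.1 = 2 placebo responders are expected, so the normal approximation is rough. Newcombe 95% intervals for an observed difference of zero are:

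- 4/40 v 2/20: −21.0 to +14.9 points
- 12/40 v 6/20: −24.9 to +21.8 points
- 20/40 v 10/20: −24.9 to +24.9 points

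The asymmetry at low rates is why the interval method should be named in advance.

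**The case against.** The strongest reply is that nothing forbidden has happened and little turns on it. Protocol 12.1 lets the SAP modify the plans. Protocol 12.6.4 calls the study exploratory. The three decision categories in SAP Section 4 rest on fibrosis response, and the middle one looks to biomarkers and safety, not to the activity index. Descriptive reporting is also the SAP's approach to clinical outcomes, biomarkers and liver stiffness. An interval of ±16 to ±30 points would settle nothing, and anyone who wants the endpoint can derive it from the listings, visibly post hoc.

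The protocol is also less than uniform. Section 8.2.2 speaks of a 2-point movement, only 12.2.2 says improvement, and 12.6.3 turns to an ordinal model without mentioning responders.

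Most of this stands as a limit on severity. The primary conclusion is untouched, the precision figures rest on assumed rates, and an openly logged and justified removal would have cured the disclosure problem. It does not remove the point. Permission to modify is not a record of modification, and the general sentence in SAP 14.1 about added detail does not disclose a removal. The uneven protocol wording is a reason for the SAP to settle the definition, yet it takes up none of the three versions. Imprecision is a reason to show an interval: the primary risk difference is reported with one at the same sample size. A risk difference with an interval needs no hypothesis test, so it fits a descriptive aim.

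**Conclusion.** The concern holds. As written, the SAP gives no sub-score, no responder and no between-arm estimate for the protocol's one named secondary efficacy endpoint, while keeping the matching objective, and Section 14 does not log the departure. This rests on the text alone.

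Two parts depend on assumptions. That component tables cannot recover the endpoint depends on the sub-score being the sum of the four items. The precision range (about 16 to 27 points half-width with 40/20, 18 to 30 with 32/16) depends on assumed common responder rates of 10% to 50% and on assumed missingness. The consequence is confined to the secondary evidence; the change should be made, but the primary analysis does not depend on it.

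**What to change.** Make these changes before unblinding.

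- **SAP 5.2.1:** state how the necro-inflammatory sub-score is formed, with the sponsor confirming whether it is the sum of the four items (0 to 18). Define a responder as at least 2 points of improvement from baseline at Month 24, following Protocol 12.2.2.
- **SAP 9.2.3:** report responder rates by arm with the risk difference and 95% confidence interval in observed cases, and name the interval method. Keep the component tables.
- **Ordinal model of Protocol 12.6.3:** either specify it (outcome categories, covariates, handling of sparse levels) or record in Section 14, with the reason, that it is dropped.

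The cost is one derived variable and one table from data already collected, plus a model specification if the ordinal analysis is kept. The drawbacks are an imprecise estimate and, for the ordinal model, sparse levels with about 60 subjects.
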